Oral glucose tolerance tests with glucose (G) and insulin (I) measured at 0, 30, 60, and 120 after glucose load to assess diabetes, insulin resistance and pancreatic β -cell function will be performed 32 (+4) weeks after study medications are started. Testing will be repeated at 56 (+4) weeks and 80 (+4) weeks after treatment start. The baseline blood samples from the OGTT will also be analyzed for liver enzymes, TSH, creatinine with eGFR (baseline and 56 weeks only), and lipid profile. Subjects will remain on treatment unless they are diagnosed with DM2 during an OGTT or a random blood test at which time final testing will be performed. They will be withdrawn from the study and they will be referred to a specialist for additional treatment of

diabetes. In subjects who complete 80 (+4) weeks of treatment, all study medications will be stopped and subjects will be asked to return for routine OGTT testing by their physician.

Primary Study Endpoint:

- An index of *insulin secretion in relation to insulin resistance (IS-SI)* will be calculated. Thus, β -cell compensatory capacity will be evaluated by the insulin sensitivity-secretion index (IS-SI) defined as the product of composite insulin sensitivity index and first-phase insulin release index (insulinogenic index).

Secondary Study Endpoint(s):

- Indexes of insulin sensitivity and secretion using the serum glucose and insulin concentrations obtained in the fasting state and during the 2hr OGTT with INS will be computed by several measures previously validated in women. Changes in insulin resistance –baseline {HOMA-IR} and composite insulin sensitivity index [ISI_{OGTT}], and pancreatic β -cell function (corrected insulin response [CIR_{glupeak}] and insulinogenic index [IGI])/HOMA-IR
- Anthropometric measurements [BMI, absolute body weight, waist circumference, waist: hip ratio,
- Cardiometabolic risk measures [lipids, liver enzymes; blood pressure]
- Development of diabetes, impaired glucose tolerance or impaired fasting glucose based on positive OGTT. Glucose tolerance will be defined as normal, impaired glucose tolerance (IGT) or diabetic according to the criteria of the American Diabetes Association.¹ Patients diagnosed with diabetes will be withdrawn from the study and referred to a specialized physician.

Biochemical assays and calculations

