Basal insulin resistance measurement The homeostasis model assessment of insulin resistance (HOMA-IR) will be calculated from fasting plasma glucose and insulin concentrations according to the report by Matthews et al.³⁶ with the formula: $HOMA-IR = FIRI \times FPG$ divided by 22.5, where FIRI is the fasting insulin concentration (microunits per milliliter) and FPG is the fasting glucose level (millimoles per liter). Lower HOMA-IR values indicate greater insulin sensitivity, whereas higher HOMA-IR values indicate lower insulin sensitivity (insulin resistance).

Indexes of insulin sensitivity from the OGTT. Originally proposed by Matsuda and DeFronzo³⁷, the composite whole body insulin sensitivity index (ISI_{OGTT}) is an insulin sensitivity index that reflects a composite estimate of hepatic and muscle insulin sensitivity determined from OGTT data. The ISI_{OGTT} is a measure of peripheral insulin sensitivity derived from the values of insulin (microunits per milliliter) and glucose (milligrams per deciliter) obtained from the OGTT and the corresponding fasting values. $ISI_{(OGTT)} = 10,000/\sqrt{[(G_{fasting} \times I_{fasting}) \times (G_{OGTTmean} \times I_{OGTTmean})]}$, where fasting glucose and insulin data are taken from *time 0* of the OGTT and mean data represent the average glucose and insulin values obtained during the entire OGTT. The

square root is used to correct for nonlinear distribution of insulin, and 10,000 is a scaling factor in the equation. ISI_{OGTT} correlates reasonably well with estimates of whole body insulin sensitivity determined by the glucose clamp. The fasting component reflects hepatic insulin sensitivity, whereas the mean of the dynamic data primarily represents skeletal muscle insulin sensitivity. This partitioning concept has recently been validated using glucose clamp studies.³⁸

Insulin secretion was estimated by two methods. Insulin secretory function will be estimated from the OGTT using the *corrected insulin response at peak glucose* ($CIR_{GluPeak}$) calculated as $(100 \times \text{Insulin}_{\text{glucose peak}}[\text{microunits per milliliter}]) / \{[\text{Glu}_{\text{glupeak}}(\text{milligrams per deciliter})] - [\text{Glu}_{\text{glupeak}}(\text{mg/dl})] - 70 \text{ mg/dl}\}$.³⁹ Corrected insulin response is a useful indicator of β -cell activity: the higher the CIR_{GluPea} , the greater the insulin secretion for the same glucose stimulus.

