The primary outcome measure is the insulin sensitivity-secretion index (IS-SI) and secondary outcome measures include changes in lipid and hepatic enzyme levels, anthropometric parameters, insulin sensitivity and pancreatic β -cell function, and glucose tolerance status. Continuous variables will be tested for normality of distribution using the Kolmogorov-Smirnov test. Natural log transformations of skewed variables will be used where necessary in subsequent analyses. For variables with highly skewed distributions, a logarithmic transformation will be done first and the geometric means reported instead. Differences in effects of drug intervention for continuous variables (in their raw or transformed state) will be compared using Subjects/Drug Treatments by trials analyses of variance (ANOVAs). This analysis provides p values for differences between groups/drug treatments (A), differences over time (B), and the interaction of group/drug treatment with time (AB). Otherwise, changes between baseline and follow-up measurements will be compared between groups by Wilcoxon's nonparametric methods. Anthropometric measurements (body weight, BMI), blood pressure, direct and indirect measurements of carbohydrate metabolism (HOMA, SI_{OGTT} , CIRgp, IGI, and ISSI), and measurements of lipid profile (total cholesterol, HDL, LDL), and liver enzymes (ALT, AST) will be considered as dependent variables. The simultaneous effect of various baseline characteristics and characteristics at certain study treatment intervals between women who did not develop diabetes and women who did during follow-up will be studied with the use of a linear multiple regression analysis. Diabetes and IGT occurrence before and after different treatment will be compared with the McNemar test (complex chi square for paired data), which formally tests for a change between the observed proportions of 2 related samples.

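### The printed formula for the corrected insulin response at peak glucose (CIR) cancels its own glucose term, so this secondary β-cell endpoint is a constant multiple of insulin with no glucose correction

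*Combined protocol and SAP*

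**What the plan says.** The formula stands in the protocol under Biochemical assays and calculations, in the part on insulin sensitivity and secretion. The numerator is "100 \times \text{Insulin}_{\text{glucose peak}}[\text{microunits per milliliter". The denominator, in braces, is "Glu}_{\text{glupeak}}(\text{milligrams per deciliter})] - [\text{Glu}_{\text{glupeak}}(\text{mg/dl})] - 70 \text{ mg/dl". Reference 39 is cited for it. The next sentence gives the interpretation: the higher the index, "the greater the insulin secretion for the same glucose stimulus".

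The index is used in two further places. Secondary Study Endpoint(s) lists it among the measures of β-cell function: "corrected insulin response [CIR_{glupeak}] and insulinogenic index [IGI])/HOMA-IR". The Statistical Analysis Plan lists it as a dependent variable, in the run "CIRgp, IGI, and ISSI", and says of continuous variables generally: "Natural log transformations of skewed variables will be used where necessary in subsequent analyses". Study Design also names the index as one to be computed from the OGTT, but gives no formula. No second definition appears anywhere.

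**The concern.** A corrected insulin response is meant to express insulin relative to the glucose that provoked it. The printed denominator subtracts peak glucose from itself, so the stimulus drops out. What remains is insulin on another scale.

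This matters in this trial because the background section describes liraglutide's actions as dependent on glucose. If the arms differ in peak glucose on treatment, insulin alone cannot separate a change in secretion from a change in stimulus. A program that follows the text would report a treatment comparison of raw insulin under the name of a corrected index. If it follows the text literally, a larger insulin response would also score as worse.

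**Working it through.** **Inputs.** The formula, its units (insulin in µU/ml, glucose in mg/dl) and its interpretation come from the protocol. The documents give neither patient values nor a worked CIR value, so there is no stated figure to reproduce. The insulin and glucose values below are assumed for illustration. The cancellation does not depend on them.

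**Algebra.** Let I be insulin at the glucose peak and G the peak glucose.

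- Literal reading: G − G − 70 = −70, so CIR = 100 × I / (−70) = −1.43 × I.
- Last two terms bracketed together: G − (G − 70) = +70, so CIR = 100 × I / 70 = +1.43 × I.

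Under both readings G has no numerical effect. It only decides which time point supplies the insulin value.

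**Numbers.** The last two columns are candidate denominators, included only to show what a surviving glucose term does. Neither is printed in the documents.

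| G | I | 100·I/(−70) | 100·I/70 | 100·I/[G × (G − 70)] | 100·I/(G − 70) |
|---|---|---|---|---|---|
| 120 | 40 | −57.14 | 57.14 | 0.667 | 80.0 |
| 120 | 80 | −114.29 | 114.29 | 1.333 | 160.0 |
| 160 | 80 | −114.29 | 114.29 | 0.556 | 88.89 |
| 200 | 80 | −114.29 | 114.29 | 0.308 | 61.54 |
| 160 | 120 | −171.43 | 171.43 | 0.833 | 133.33 |

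**Against the stated interpretation.**

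1. Glucose correction: at I = 80, the women with G = 120, 160 and 200 get identical scores under both readings of the printed formula. They reached the same insulin at very different stimuli, and the index cannot tell them apart.
2. Direction: at G = 160, raising insulin from 80 to 120 moves the literal index from −114.29 to −171.43. More insulin gives a lower score, which is the reverse of the text. With +70 the direction is right (114.29 to 171.43).
3. Log transformation: every literal value is negative, so the natural log is undefined. With +70 the problem disappears.

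**Can the intended formula be recovered from the text?** Both candidate columns fall as G rises at fixed I, and rise with I at fixed G, provided that G exceeds 70. So both fit the stated interpretation, yet they are not interchangeable. Compare (G = 120, I = 40) with (G = 160, I = 80):

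- Product: 4000 / (120 × 50) = 0.667 against 8000 / (160 × 90) = 0.556, so the first woman ranks higher.
- Difference: 4000 / 50 = 80.0 against 8000 / 90 = 88.89, so the second ranks higher.

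**Reach.** IS-SI is the product of IGI and ISI_OGTT. IGI uses the 0 to 30 minute increments, and HOMA-IR uses fasting values. The sample size rests on IS-SI. CIR enters none of them.

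**The case against.** **It may be a conversion error.** The formula was read from a PDF by a program, and the defect hangs on one operator and one pair of brackets. The same paragraph also gives the index's label in two spellings. This cannot be excluded, and the PDF should be looked at first. On the other side, the multiplication sign in the numerator of the same formula was read correctly, so a misread operator is possible but not shown.

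**The sign may be right.** With the last two terms bracketed together, the reversed direction and the log problem both vanish. The plan also takes logs only where necessary and provides Wilcoxon methods otherwise. This stands: a reader might infer that the index is reversed whatever the bracketing, and the documents do not support that. The lost glucose correction remains under both readings. It might be said that with +70 the interpretation still holds among women who share a peak glucose. That is true of raw insulin as well, and it is not a correction.

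**The replacement looks obvious.** A reader might infer that the denominator should simply be G × (G − 70). No section of the documents contains that product, and the stated interpretation fits G − 70 equally well. The product form is an assumption until reference 39 has been read.

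**It is minor.** CIR is one of several secondary indices, and its inputs are collected in any case. The index can be recomputed at any time, and an output that is negative throughout would be conspicuous. All of this stands and lowers the severity. The +70 reading, however, would give plausible positive values and no warning.

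A reader might also infer that eligibility was affected, because β-cell dysfunction is a route into the trial and CIR is among the screening indices. No CIR cut-off is given, so the documents do not show this.

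**Conclusion.** The concern holds for the formula as printed. CIR reduces to −1.43 × insulin read literally, or +1.43 × insulin with the alternative bracketing. Neither carries any glucose correction, contrary to the protocol's own description of the index. The reversed direction and the failure of the log transformation hold only under the literal reading.

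The damage is confined to one secondary β-cell endpoint and its analysis as a dependent variable. The primary endpoint, IGI/HOMA-IR and the sample size are untouched, and the trial's main conclusion is not threatened by this point. The documents also do not show how the analysis program was written, so nothing here says that any result was computed wrongly.

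The conclusion rests on the formula having been read correctly from the PDF. It does not rest on the illustrative values. This should be fixed before analysis.

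**What to change.** 1. Compare the printed formula with the source PDF, to rule out a misread operator or bracket.
2. Compare it with reference 39, the source the protocol cites for the index.
3. Put the verified denominator in the protocol and the analysis program, with unambiguous brackets and units. Two conditions should hold: peak glucose must not cancel, and the index must rise with insulin at a given glucose. G × (G − 70) is one candidate, but G − 70 meets the same conditions, so the choice should come from the source and not from inference.
4. Add one worked example to the program specification, so that the code can be tested against it.

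The cost is one corrected formula and a check of one reference. No new data, visits or assays are needed, because the OGTT glucose and insulin values are already collected.

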The reason for a subject discontinuing from the study will be recorded in the patient chart. A discontinuation occurs when an enrolled subject ceases participation in the study, regardless of the circumstances, prior to completion of the protocol. The investigator must determine the primary reason for discontinuation. Withdrawal due to adverse event will be distinguished from withdrawal due to insufficient response according to the definition of adverse event noted earlier. The final evaluation required by the protocol will be performed at the time of study discontinuation. The investigator will record the reason for study discontinuation, provide or arrange for appropriate follow-up (if required) for such subjects, and document the course of the subject's condition. They will also to be reported to Woman's Hospital Foundation Institutional Review Board at [contact] and Woman's Health Research Department at [contact].

Sample Size Computation and Power Analysis

A priori sample size analysis was performed using the online calculator provided by the Massachusetts General Hospital Mallinckrodt General Clinical Research Center (http://hedwig.mgh.harvard.edu/sample_size/size.html). Because the possible advantages of combination treatment over metformin alone rely on the presumed positive effects of liraglutide on pancreatic β -cell function parameters, we used the difference in a surrogate marker of insulin secretion relative to insulin resistance as the primary outcome for sample size analysis. An experimental design including a total of 118 patients would have power above 0.80 to detect differences in the IS-SI index between treatments such as those previously reported using a similar experimental design.⁴⁶

We plan on recruiting 150 overweight women with a recent history of GDM to be studied. The estimated enrollment: of 75/group for an average follow up of 60 weeks of treatment (range 32-84 weeks) will be our intent-to-treat population. This sample size is projected to provide power ≥ 0.8 to detect a $\geq 20\%$ difference in insulin action indices between treatment groups at a median follow-up of 24 months. The calculation was adapted to allow for significant dropout rate (20-22%) for completion of the full trial of 80 (+4) weeks of treatment. Subjects who drop out of the trial will not be replaced

Statistical Analysis Plan:

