All analyses will be conducted with subjects assigned to their initial treatment group, using all available data for the period of follow-up relevant to the particular analysis. Data will be analyzed on the basis of intention to treat and also on completed treatment parameters where relevant. Differences of $P < 0.05$ will be considered statistically significant. Results will be reported as mean \pm standard error of the mean (S.E.M) for quantitative variables and percentages for categorical variables unless otherwise noted. We will perform all statistical analyses using SPSS 15.0 for Windows (SPSS, Inc.; Chicago, Ill).

Study Drugs

Description

Both active drug (Liraglutide 6.0 mg/ml injection) and placebo will be supplied by Novo Nordisk A/S. as a pre-filled pen for subcutaneous injection. Each liraglutide pre-filled pen contains 18 mg/3 ml (6 mg/ml) and will deliver 30 doses of 0.6 mg; 15 doses of 1.2 mg or 10 doses of 1.8 mg; the placebo pen will deliver equal volumes of vehicle solution only. Liraglutide and placebo are visually identical.

Metformin Hydrochloride XR (extended-release) in 500 mg strength oral tablets will be purchased in bulk through the Woman's Hospital Infusion Pharmacy. Metformin hydrochloride XR is combined with a drug release controlling polymer so that drug is released slowly from the dosage form. The medication will be allocated into appropriate patient dosage regimens by the hospital pharmacy personnel. Dosage of metformin XR will be prescribed according to standard directions and not exceeding the maximum recommended daily dose in adults of 2000 mg.

Trial Supplies

Double-blind Liraglutide or placebo

Liraglutide 6.0 mg/ml or placebo solution for injection in a 3 mL pre-filled pen will be supplied by Novo Nordisk A/S. The pre-filled pen will be provided as a pen-injector. The Investigator will provide each subject with Direction for Use for the liraglutide pen-injector at each dispensing visit.

Packaging and Labelling of Trial Products

Liraglutide and placebo will be packed and labelled by Novo Nordisk A/S and provided in non subject specific boxes. Labelling will be in accordance with Annex 13, local law and trial requirements.

Storage, Handling, Accountability and Destruction of Trial Products

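### In its usual four-visit form the named ANOVA would analyse IS-SI in completers only, although the plan promises intention to treat on all available data and gives no rule for incomplete women

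*Combined protocol and SAP*

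**What the plan says.** IS-SI is the primary outcome. The Laboratory Measures text sets a baseline and three follow-up measurements. The follow-up paragraph under Randomization and Allocation has the first OGTT at week 32 and adds: "Testing will be repeated at 56 (+4) weeks and 80 (+4) weeks after treatment start".

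The Statistical Analysis Plan says that drug effects on continuous variables, raw or transformed, "will be compared using Subjects/Drug Treatments by trials analyses of variance (ANOVAs"). The ANOVA is to give p values for "differences between groups/drug treatments (A), differences over time (B), and the interaction of group/drug treatment with time (AB"). None of the three is named as primary. A fallback follows the normality and transformation text: "changes between baseline and follow-up measurements will be compared between groups", by Wilcoxon methods. It names no visit.

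On populations, analyses go by initial group, "using all available data for the period of follow-up relevant to the particular analysis". Then: "Data will be analyzed on the basis of intention to treat and also on completed treatment parameters where relevant".

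Sample Size Computation and Power Analysis states that "75/group for an average follow up of 60 weeks of treatment (range 32-84 weeks) will be our intent-to-treat population". Enrolment was adapted to "allow for significant dropout rate (20-22%) for completion of the full trial of 80 (+4) weeks of treatment", and dropouts are not replaced.

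Women diagnosed with type 2 diabetes (DM2) have final testing and leave the study. The Discontinuations section requires a final evaluation of anyone who stops. No section says whether or at which visit these results enter the IS-SI analysis, and none gives an imputation method, a mixed model or any other rule for a missing visit.

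**The concern.** A subjects-by-trials ANOVA in its usual form needs a value at every occasion and drops any woman who lacks one. The plan's own intention-to-treat population contains women followed for only 32 weeks, who have no week-56 or week-80 value. The plan lists intention to treat and completed treatment as two analyses, yet with this method both could be the same set of completers under two names.

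Some of the loss is plausibly related to the outcome. Women leave at DM2 diagnosis, and the section on insulin sensitivity and secretion itself says that the product of insulin secretion and ISI predicts onset of type 2 diabetes. Completers would then be selected partly on the primary outcome, possibly to a different degree in each arm.

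**Working it through.** **Inputs.** From Sample Size Computation and Power Analysis: 118 women needed, 150 enrolled (75 per arm), 20-22% dropout. From Laboratory Measures: four occasions. Not given: the IS-SI difference and SD, dropout by arm, and the expected DM2 rate.

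1. **The plan's figure.** 118/(1 - d) gives 147.5 (148) at d = 0.20, 149.4 (150) at 0.21 and 151.3 (152) at 0.22. Conversely, 1 - 118/150 = 21.3%. The 150 is reproduced, and the 118 are the women expected to complete.

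2. **Women omitted by a four-visit ANOVA.** 150 × 0.20 = 30 and 150 × 0.22 = 33, leaving 120 and 117. If dropout has an equal rate in each of the three follow-up intervals (assumed), about 532-539 visit records exist. Completers supply 4 × 117 = 468 to 4 × 120 = 480.

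3. **Shorter windows.** If dropout is spread evenly over 80 weeks (assumed), an ANOVA through week 56 would omit 30 × 56/80 = 21 to 33 × 56/80 = 23. If nobody leaves before week 32, as the stated follow-up range implies, an ANOVA of baseline and week 32 would omit essentially none. The plan names neither window.

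4. **Power.** Two-sided 0.05 is assumed. With 59 per arm and 80% power, the standardised difference is d = (1.960 + 0.842) × √(2/59) = 0.516 (0.520 by the t-test). Power = Φ(d√(n/2) - 1.960) is 0.807 at 60 per arm and 0.797 at 58.5, against 0.885 at 75. Completers therefore keep about the planned 0.80.

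5. **Bias, by simulation under assumptions.**
   - Control-arm DM2 rate: the Background gives 12.1-13.1% a year on placebo and a 31% reduction with metformin. So 12.1 × 0.69 = 8.3 to 13.1 × 0.69 = 9.0% a year, and × 56/52 gives 9.0-9.7% by week 56. This mixes populations and is only indicative, so 8% and 10% were used.
   - Effect: 0.52 SD, constant or growing to that size. Non-completion: 21% including DM2 withdrawals, which occur at weeks 32 and 56. Other dropout is random.
   - Data: 400,000 women per arm, with equal-correlation, autoregressive (AR) or random-slope structure. The correlation of the DM2 trigger with IS-SI is 0.5 or 0.7.

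Loss of effect in completers, against the same contrast with nothing missing:

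| Contrast | Trigger correlation 0.5 | 0.7 |
|---|---|---|
| Group by time, equal-correlation or AR | 0.4-1.8% | 0.8-3.1% |
| Group by time, random slopes | 1.1-3.7% | 2.4-6.2% |
| Week-80 change, equal-correlation or AR | within 1% | within 1% |
| Week-80 change, random slopes | 0.2-3.8% | 0.7-6.2% |
| Overall group effect A | 4.1-8.8% | 8.5-14.8% |

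A suffers most because it compares levels, and removing women with low IS-SI shifts the level. A change score cancels most of that shift. A is also diluted: with nothing missing, a constant effect gives (0 + 3 × 0.52)/4 = 0.39 SD, because baseline is averaged in. At trigger correlation 0 every contrast stays within 0.8% of no loss.

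6. **Precision.** In 3,000 simulated trials per setting (75 per arm, 21% random loss), the week-80 standard error in baseline-adjusted completers was 1.01-1.03 times that of the mixed model.

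**The case against.** **The completers analysis is inferred.** The plan gives no number of visits for the ANOVA and requires all available data. Listwise deletion belongs to the usual wide-format procedure. Fitted in long form with subject as a factor, the ANOVA accepts incomplete women. In a simulation with similar assumptions that version gave a group-by-time effect of 0.522-0.530 against a true 0.52, while completers gave 0.507-0.516. This stands, and it is why the point is conditional. The plan does not ask for that form, though, and even then it would not place final evaluations or name a contrast.

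**The bias is small.** For group-by-time and change from baseline it is, and every percentage rests on assumed rates and correlations. The only sizeable figure is for A, which the plan does not call primary. It does not exclude A either.

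**The Wilcoxon comparison of changes could serve.** It is offered for variables unsuited to ANOVA, not for missing visits.

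A reader might also infer four stronger things that the documents do not support:
- *The trial loses planned power.* Enrolment was already inflated for this dropout.
- *The 60-week average means many more than 33 women are lost.* That average sits badly with the stated dropout rate, but it is a separate inconsistency in the sample-size text. The dropout allowance is the plan's figure for completion.
- *DM2 withdrawals come on top of the 20-22%.* That rate is for completing the full trial, and the Discontinuations section counts any early end of participation whatever the reason. DM2 withdrawals most naturally fall inside it.
- *Discontinuation OGTTs will be discarded.* Neither final testing nor the final evaluation is said to include an OGTT, and nothing says that the results go unused. What is missing is the rule.

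**Conclusion.** The point holds in conditional form. In its usual four-visit form the named ANOVA omits 30-33 of 150 women at the planned dropout, so it does not deliver the intention-to-treat analysis on all available data that the plan promises. The plan neither asks for a form that would, nor says how incomplete women and their final evaluations enter.

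The main consequence is the population analysed. Power is essentially as planned. Bias is about 0-3% for group-by-time or change from baseline, up to about 6% with random slopes, and about 4-15% for A. These figures assume a 0.52 SD effect, 21% non-completion, 8-10% control DM2 withdrawal by week 56 and trigger correlations of 0.5-0.7. In these scenarios the effect shrinks, but the real direction is uncertain because dropout by arm is not given. If loss is random there is no bias. Severity: minor to moderate.

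**What to change.** - **Primary IS-SI analysis.** Use a likelihood-based mixed model for repeated measures, on the log scale if skewed, with all randomised women and every observed visit. Enter baseline as a response with a common mean across arms, so that women without follow-up stay in. Include treatment, categorical visit and treatment-by-visit, and name one contrast in advance, for example week 80.
- **Final evaluations.** Where one includes an OGTT, assign it to the nearest planned visit within a pre-set window. A scheduled value takes priority if both exist. Never carry it to a later visit.
- **Sensitivity analysis.** Add one for women withdrawn for DM2, for example ranking them lowest at week 80 and using the Wilcoxon method already named. State a rule for other dropouts too.
- **Completed treatment.** Keep the ANOVA and label it as this analysis.

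The cost is SAP wording and a little extra analysis, with no new visits or patients and no change to any clinical rule. The model assumes data missing at random. For DM2 withdrawals that is more plausible when the OGTT at diagnosis is entered, and the sensitivity analysis probes it. Precision improves by only about 1-3%, so the gain is mainly that the promised analysis is carried out.

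### The plan does not say which visit or which ANOVA p-value tests the primary IS-SI hypothesis, and the candidate p-values can give different answers

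*Combined protocol and SAP*

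**What the plan says.** Under Primary Study Endpoint, beta-cell compensation "will be evaluated by the insulin sensitivity-secretion index (IS-SI) defined as the product of composite insulin sensitivity index and first-phase insulin release index". No visit, change score or average is attached to it. The OGTT schedule in Study Design gives four measurements: baseline and weeks 32, 56 and 80, each follow-up visit with a 4-week allowance.

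The Statistical Analysis Plan repeats IS-SI as the primary outcome and analyses continuous variables by a treatment-by-trials ANOVA: "This analysis provides p values for differences between groups/drug treatments (A), differences over time (B), and the interaction of group/drug treatment with time (AB". It does not say which p-value answers the primary objective, or whether baseline is one of the trials. In the nonparametric alternative, "changes between baseline and follow-up measurements will be compared between groups" by a Wilcoxon method, again with no visit named.

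Subjects stay in their assigned group, "using all available data for the period of follow-up relevant to the particular analysis". Then: "Data will be analyzed on the basis of intention to treat and also on completed treatment parameters where relevant". P-values below 0.05 "will be considered statistically significant".

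Sample Size Computation and Power Analysis says 118 women give power above 0.80 for IS-SI, and plans 150. "The calculation was adapted to allow for significant dropout rate (20-22%) for completion of the full trial of 80 (+4) weeks of treatment". The 75 per group are called the intent-to-treat population, "for an average follow up of 60 weeks of treatment (range 32-84 weeks". The same paragraph ties a power statement to a median of 24 months of follow-up.

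**The concern.** Two p-values in the stated analysis speak to treatment, and they ask different questions. A asks whether the arms differ on average over the trials in the model. AB asks whether the arms' profiles over time differ in any way. With baseline among the trials, A averages in a visit at which no drug has been given, and AB is significant for any departure from parallel profiles, whatever its direction or timing. Without baseline, A is a clean on-treatment comparison, and AB has nothing to detect if the effect is constant. Which p-value tests liraglutide therefore depends on a choice the plan does not record.

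That choice could be made after the data are seen. The overview calls the study a pilot, but the primary objective asks whether adding liraglutide is more effective, the comparison is powered above 0.80, and it is judged at 0.05. A verdict on the drug will rest on it.

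A related point affects the remedy. A classical trials ANOVA needs every visit from every woman, which sits badly with the commitment to use all available data. Women diagnosed with DM2 leave the study early, and the protocol says that an index of this kind predicts DM2, so their absence may not be random.

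**Working it through.** **Inputs.** From the documents: 118 women for power, 150 enrolled, 1:1 allocation, 20-22% dropout, alpha 0.05, four measurement times, at most 84 weeks. Assumed: two-sided testing, and the correlation r between visits (0.3, 0.5, 0.7), because the documents give no SD or correlation for IS-SI. All power figures are therefore illustrative.

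**1. The plan's own figures.** 118/(1 - 0.20) = 147.5 and 118/(1 - 0.22) = 151.3. The planned 150 implies 1 - 118/150 = 21.3%, so the inflation reproduces and the 118 are the expected week-80 completers. The 118 itself cannot be reproduced, because no effect size or SD is given. At 59 per arm, 80% power and two-sided 0.05, a t-test detects 0.52 SD. That is the effect used below.

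**2. Follow-up.** 84 weeks x 7/30.44 = 19.3 months. A median of 24 months (about 104 weeks) cannot occur.

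**3. Baseline as a trial, sustained effect of 0, 0.52, 0.52, 0.52 SD.**
- A estimates (0 + 3 x 0.52)/4 = 0.39 SD, which is 0.75 x 0.52. Its SE is sqrt[2 x ((1 + 3r)/4)/59] = 0.127, 0.146, 0.162.
- AB has 3 and 348 df. The deviations from the mean effect are -0.39, 0.13, 0.13, 0.13, with sum of squares 0.2028. Noncentrality = (59/2) x 0.2028/(1 - r) = 8.5, 12.0, 19.9.
- Under equal correlations A and AB are independent, so P(disagree) = pA(1 - pAB) + pAB(1 - pA).

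| r | Power of A | Power of AB | One significant, the other not |
|---|---|---|---|
| 0.3 | 0.86 | 0.68 | 37% |
| 0.5 | 0.76 | 0.83 | 33% |
| 0.7 | 0.67 | 0.97 | 34% |

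Simulation agrees to within about 1 percentage point. With autoregressive correlation 0.7, simulation gives 0.73, 0.86 and 32%.

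**4. Post-baseline visits only, same effect.** A estimates the full 0.52 SD with SE sqrt[2 x ((1 + 2r)/3)/59] = 0.134, 0.150, 0.165. Power is 0.97, 0.93, 0.88 (autoregressive 0.90). AB rejects in about 5%.

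**5. Effect at week 32 only (0, 0.52, 0, 0), baseline as a trial.** The deviations are 0.39, -0.13, -0.13, -0.13, so the sum of squares is again 0.2028. Under equal correlations AB has exactly the same power as in step 3 (0.68, 0.83, 0.97), although nothing is left at week 80. A week-80 ANCOVA on such data rejects in 5%. AB cannot separate the two patterns.

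**6. No drug effect, success allowed on A or AB.** 1 - 0.95^2 = 0.0975 under equal correlations (simulated 9.7-9.8%). With autoregressive 0.7 it is 10.7%, because AB alone then rejects 6.1%; after a Greenhouse-Geisser correction it is 9.3%.

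**7. A designated test.** Mixed model adjusted for baseline, 75 per arm falling to 70, 64 and 59 at the three visits (assumed, unrelated to outcome), sustained 0.52 SD. Week-80 power is 0.85, 0.91, 0.98 (autoregressive 0.87). The on-treatment average has at least 0.99.

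**The case against.** **Intention to treat already leads.** This largely stands. The 75 per group are named the intent-to-treat population, subjects are analysed as assigned, and the completed-treatment analysis is an addition where relevant. A reader might infer that the two sets compete on equal terms, but the text does not support that. Only the label of primary is missing.

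**A is the obvious test.** It is, if only post-baseline visits are trials (step 4). The plan does not say so, and a trials ANOVA that also reports differences over time more naturally includes baseline. The dilution in step 3 is therefore conditional, and both readings have to be shown.

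**The error rate is 5%, not 10%.** A reader might infer that the plan runs at 10%. It contains no either-or success rule, so the documents do not establish that figure. They do not exclude such a rule either.

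**The transient effect is contrived.** It is an extreme pattern, chosen to show what AB can and cannot tell apart. It is not a forecast.

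**Week 80 is implied by the sample size.** The dropout allowance points there, but the same paragraph gives an average of 60 weeks on treatment, which fits a comparison over all visits as well. Neither is named as the analysis time.

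**Women who leave are not simply lost.** The plan promises all available data and requires final testing at withdrawal. It does not say how those tests enter an ANOVA with fixed visits.

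**Conclusion.** The gap is real and should be closed before unblinding. No visit or contrast is named for IS-SI, and neither A nor AB is designated. This needs no assumption; it is what the text omits.

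Its size depends on an unstated choice. With baseline as a trial, A recovers three quarters of a sustained effect, and A and AB disagree in roughly 32-37% of trials at 59 per arm and 0.52 SD, over the correlations tried. With post-baseline visits only, A carries the full effect at power 0.88-0.97 and is the natural test. An error rate near 10% applies only if either p-value could be claimed.

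The contradiction between a 24-month median and a 19.3-month maximum is arithmetic and rests on the documents alone.

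**What to change.** Designate one primary test before unblinding: the intention-to-treat difference between arms in ln(IS-SI), adjusted for baseline ln(IS-SI), from a mixed model using all available post-baseline OGTTs, two-sided 0.05, reported as a ratio of geometric means with 95% CI. Name one contrast: week 80 (+4), to which the dropout allowance points, or the on-treatment average, which has more power if the effect is sustained. Label A, B, AB, the other visits, the Wilcoxon test and the completed-treatment analysis as secondary.

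The amendment should also:
- state how final tests at withdrawal enter the model, including those before week 16, which lie closer to baseline than to week 32;
- add a sensitivity analysis for DM2 withdrawals that does not assume missing at random;
- fix, blind to arm, how an undefined insulinogenic index or logarithm is handled, and report counts by arm. The rule should not award the best value when glucose fails to rise by 30 minutes: the background says GLP-1 inhibits gastric emptying, so such a rule could favour liraglutide;
- restate the follow-up in the power statement to agree with the 80 (+4) week treatment period.

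**Cost.** A protocol amendment with prior written IRB approval, and no new data or visits. The main analysis assumes missing at random. If the effect is sustained, week 80 has somewhat less power than the on-treatment average (0.85-0.98 against at least 0.99, under the assumptions in step 7).
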